5.3 Strategies for Recruitment and Retention

Practices:

During the pilot study phase, Medical Directors from the 26 RCC practices were invited to participate in an informational webinar led by the PI and a Co-Investigator (Medical Director of the RCC) to learn more about the opportunity for their practice to participate in the study. The PI, Project Manager and Study Coordinator then met with interested providers at practices which met the inclusion criteria. The 18 practices which met the inclusion criteria have provided letters of support indicating their commitment to participation. One practice will serve as a backup practice and has also given a letter of support.

Retention strategies for the practices will include regular contact between the study staff and practice staff to ensure any issues which may arise are addressed immediately, and tailoring study logistics based on practice flow as learned from our two pilot practices.

Practices also receive compensation for facility use for the trainings, for research staff being present at the practices to complete study visits, and for the structured interviews and debriefing sessions.

Providers:

During the pilot study phase, all pediatricians and nurse practitioners of the 18 practices were invited to attend the informational meetings which took place at their individual practices. The PI, Project Manager and Study Coordinator briefed the providers regarding the study goals and logistics. A total of 67 providers from the 18 practices to be randomized who met the inclusion criteria will participate in the main trial. An additional information session for providers will be held at each practice prior to the start of the main trial. At this time, informed consent will be obtained from each pediatrician/nurse practitioner participant.

Retention strategies for providers include Continuing Medical Education (CME) credits for didactic OH education and Maintenance of Certification (MOC) credits for quality improvement initiatives. Twenty five (25) MOC credits have been approved by the American Academy of Pediatrics (AAP) for physicians participating in this dental project. The study staff will maintain regular contact with providers to address any concern or issue that may arise.

CME credits will also be available for providers upon completion of briefing seminar.

Parent/caregivers:

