12.2 Sample Size Considerations

The study design will involve a cluster randomization to two arms:

1. Bundled (Practice + provider) interventions, 2. Enhanced usual care. The assumed response rates (proportion of children who have dental attendance) are Arm A: 0.46 (The dental utilization reported among Medicaid-enrolled children by Vujicic and Nasseh, 2015 was 48%, but we used 46% to be conservative), Arm B: 0.30 (based on pilot study where 30% of parent reported routine dental visit for child in the past year).

Eighteen practices (comprising the clusters) will be included in the study. Practices will be randomized to one of the two arms using a restricted randomization scheme with the constraint that 9 practices will be assigned to each arm. This approach will involve the computation of a balance score (for each candidate randomization) based on marginal differences in three key practice-level variables: % Medicaid-enrolled patients [20% to 40% and >40%], ratio of patients to providers, county [Cuyahoga vs. other]. We use the first generated (constrained) randomization that provides good balance according to a pre-selected balance criterion; it may be reasonable to require perfect marginal balance, if (as we expect) there are a reasonably large number of randomizations that yield this.

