The primary objective is to compare dental care attendance between the two arms. For simplicity in the power calculation we consider the binary outcome of any dental attendance in the two year period of follow-up. Dental attendance will be based on a single summary score (number of years - out of two - in which the child visits the dentist at least once a year). We thus suppose the use of a two-sided 0.05 alpha level z test (with pooled variance) for a difference in proportions. We assume, as a rough approximation, that the study will recruit an equal number of patients in each practice. Making conservative allowances for an intra-cluster (within-practice) correlation (ICC: in the binary dental attendance outcome) of 0.04 and a 25% drop-out rate, a sample size of 512 participants per arm (total n= 1024) will provide an estimated 80% power to detect the above difference in proportions. Alternatively, this sample size (actually 438 per group) will provide 90% power to detect this same effect size if the ICC is only 0.02. If the intervention effect is only 0.12 (0.42 versus 0.30), a sample size of 457 per group (914 total) will still provide 80% power with a dropout rate of 25% if the ICC is only 0.01. For the purposes of this study, a sample size of 512/arm (n=1024) will be recruited.

For sample size estimates, an important secondary outcome will be incidence of new decayed or filled teeth (dft). Mean dft is hypothesized to decrease for Arm A relative to Arm B. Our

previous data (Lee et al. 2015) among 5 to 7 year old low-income children suggests a mean dft for usual care of 4.5 (standard deviation = 7) which we assume to be a reasonable value for the enhanced usual care arm in the present study. We assume the same standard deviation for the new intervention group, assuming normally distributed responses for the power calculation. In fact, as dft is a count (possibly following a distribution such as Poisson or negative binomial) it is likely that the standard deviation will decrease with the mean, making our approach conservative (McCullagh and Nelder 1989).

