12.4 Final Analysis Plan

Primary Statistical Analysis:

Descriptive statistics will include frequencies (categorical variables) and means (continuous variables) of baseline covariates among the three intervention groups. Chi-square tests (for categorical variables) and t- or F-tests (via ANOVA for continuous variables) will be performed in a preliminary analysis to test for group differences.

For the primary outcome, we will use as an overall dental attendance score the number of years (over the two years of follow-up) in which the child visited the dentist. This will be an ordinal outcome with possible scores of 0, 1 or 2. To assess the intervention effect, we will use a generalized estimating equations (GEE) approach, with practices as clusters, based on a proportional odds marginal model. The model covariates will include an intervention indicator variable (equal to 1 for bundled intervention, 0 for enhanced usual care) and a set of baseline variables representing potential confounders. A standard error correction (for example, the method by Morel et al. 2003) will be used to adjust for a small number of clusters and 95% confidence intervals will be computed. This will be an intent-to treat analysis as all randomized participants providing the necessary measurements – regardless of any lack of compliance – will be included in the analysis.

In the event of missing data (for either year) for dental attendance, we will conduct sensitivity analyses by imputing responses under conservative assumptions (favoring the null hypothesis) and re-running the analysis described above on the completed data.

Analysis of Secondary Outcomes: Summary statistics (including means and standard errors) for secondary outcomes will be calculated by intervention group. The same approach as above will be used for binary or ordinal secondary outcomes (oral hygiene, frequency of sweet snacks and beverages). Namely, ordinal outcomes for each variable will be defined that summarize outcomes over time. For continuous outcomes (e.g., OH quality of life, cost), the above method

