help reveal the importance of each of the multiple components of the bundled intervention. For example, we can estimate the proportion of intervention effect mediated by 'compliance' with regard to EMR documentation. A relatively high mediation proportion will suggest efficacy of the corresponding component.

We have previously developed a generalized causal mediation (GCM) analysis methodology and an accompanying R package (Albert & [name], 2011; Albert, Unpublished; Cho & Albert, Unpublished) which we will use to estimate and test each path effect and its proportion of the total intervention effect. The GCM method allows mediators and final outcomes of different types, including continuous, binary, and count (assumed to have normal, Bernoulli, and Poisson or negative binomial distributions, respectively). These options will accommodate the mediators and final outcome (dental attendance, summarized as a binary response) in our model. Each outcome (including mediators) is modeled using a generalized linear model that includes as covariates possible baseline confounders as well as causally preceding variables according to the causal model (as in Figure 4.2.1). The method uses an extended version of the mediation formula and assumes an extended version of the sequential ignorability assumption. (Albert et al., Unpublished) Bootstrap resampling is used to compute confidence intervals and a cluster bootstrap option is available to account for unexplained between-cluster (e.g. provider) variability.

Adjustment for Baseline Characteristics: Estimated intervention effects will be adjusted for the following baseline socio-demographic variables: child's age, race, and caregiver SES, education, and marital status.

Model Assumptions: We will assume that the probabilities of dental care receipt follow a logistic regression model with the included covariates and random effects. Per the standard approach, random effects will be assumed to be independent, normally distributed, and outcomes assumed conditionally independent given the random effects. If multiple random effects (e.g., for different cluster levels) are used, they will be assumed to be independent. For secondary outcomes, analogous assumptions, including the assumption of the correct link function, will be made.

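### The resampling unit for the mediation confidence intervals is not fixed, and the only cluster level named for them, the provider, lies below the randomised practice

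*Combined protocol and SAP*

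**What the plan says.** Practices are the unit of allocation. Sections 5.4.1 and 12.2 describe a "restricted randomization scheme with the constraint that 9 practices will be assigned to each arm". The power calculation in section 12.2 allows for an "intra-cluster (within-practice) correlation (ICC: in the binary dental attendance outcome) of 0.04 and a 25% drop-out rate". The primary analysis in section 12.4 is a GEE "with practices as clusters", with a standard-error correction for the small number of clusters.

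The mediation part of section 12.4 is looser. Each mediator and outcome is fitted with a generalized linear model, and confidence intervals for path effects and proportions mediated come from bootstrap resampling. On clustering it says only that "a cluster bootstrap option is available to account for unexplained between-cluster (e.g. provider) variability". Practice is not named there, use of the option is not promised, and no small-cluster correction is given. The paths include variables measured on the practice itself, such as EMR documentation, readiness and climate.

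**The concern.** The mediation models as described carry no clustering term, so the bootstrap is the only stated place where clustering enters these intervals. Its resampling unit therefore decides whether they are valid. The intervention indicator is constant within a practice. Resampling children, or the 67 providers, treats units that share one allocation and one set of practice-level mediator values as independent. The primary analysis does not do this.

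At stake are secondary objective 2 (section 3.1) and the plan's stated route to judging which part of the bundle works. Section 12.4 intends to test each path effect and its share of the total effect, and to read a relatively high mediated share as a sign that the component is efficacious. Intervals that are too narrow would make such shares look better established than they are. Leaving the unit open also allows a choice, once data are in hand, among procedures that give materially different widths.

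**Working it through.** **Inputs.** From section 12.2: attendance 0.46 against 0.30, 512 per arm, 9 practices per arm, within-practice ICC 0.04, 25% dropout, two-sided alpha 0.05. From section 5.3: "A total of 67 providers from the 18 practices to be randomized". From Table 4.1.1: providers per practice, 1 to 8. The documents do not give the split of the ICC between practice and provider, the ICCs of the mediators, or the size of any path. These are assumed below and shown as a range.

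**Step 1: the plan's own figure.** Evaluable children: 512 × 0.75 = 384 per arm, or 384/9 = 42.67 per practice. Design effect: 1 + (42.67 − 1) × 0.04 = 2.667. Effective n: 384/2.667 = 144 per arm, and the pooled z test then has 80.2% power. Solving for n at 80% power gives 505 per arm. Section 12.2 says "a sample size of 512 participants per arm (total n= 1024) will provide an estimated 80% power", so the figure reproduces, and it does so with practices as the clusters. The two alternatives in that section also reproduce: 435 against the stated 438 at ICC 0.02, and 457 against 457 at ICC 0.01.

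**Step 2: between-arm contrast, by resampling unit.** Evaluable children per provider: 768/67 = 11.46. Let s be the share of the ICC that lies at practice level.

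- Correct design effect = 1 + 41.67 × 0.04 × s + 10.46 × 0.04 × (1 − s)
- Design effect seen by a provider bootstrap = 1 + 10.46 × 0.04 = 1.419
- Design effect seen by a child bootstrap = 1
- SE ratio r = √(design effect seen / correct design effect)
- Coverage = 2Φ(1.96 r) − 1

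| ICC 0.04, share at practice level | Correct design effect | Provider: r, coverage | Child: r, coverage |
|---|---|---|---|
| All (s = 1) | 2.667 | √(1.419/2.667) = 0.73, 85% | √(1/2.667) = 0.61, 77% |
| Half (s = 0.5) | 2.043 | √(1.419/2.043) = 0.83, 90% | 0.70, 83% |
| None (s = 0) | 1.419 | 1.00, 95% | 0.84, 90% |

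Provider caseloads are unequal. With equal numbers of children per practice and the provider counts of Table 4.1.1, the size-weighted caseload is 16.1, and the s = 1 provider row becomes r = 0.78, coverage 87%. With s = 1 and a smaller ICC, r for provider resampling is 0.81 to 0.84 at ICC 0.02 and 0.88 to 0.90 at ICC 0.01 (simple and size-weighted caseloads).

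**Step 3: the quantity section 12.4 will actually report.** An indirect effect is a product of paths, and the mediator-to-outcome path also draws on variation within practices, so step 2 need not carry over. A simulation used 18 practices, 67 providers distributed as in Table 4.1.1, 43 children per practice, 400 data sets and percentile intervals from 200 resamples within arm. Assumed: continuous mediator and outcome, residual ICC 0.04 for both, and path coefficients of 0.5 (arm to mediator), 0.4 (mediator to outcome) and 0.2 (direct).

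| Share of ICC at practice level | Indirect-effect coverage: practice / provider / child | Total-effect coverage: practice / provider / child |
|---|---|---|
| All | 91% / 86% / 81% | 91% / 82% / 73% |
| Half | 90% / 88% / 83% | 90% / 89% / 81% |
| None | 93% / 96% / 92% | 91% / 93% / 87% |

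With all clustering at practice level, the mean interval width for the indirect effect was 0.179 (practice), 0.150 (provider) and 0.131 (child), against 3.92 × the empirical SD = 0.194. The Monte Carlo standard error of a coverage near 86% is √(0.86 × 0.14/400) = 1.7 points.

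**The case against.** The text describes what the software can do. It selects no unit, gives the provider only as an example, and does not exclude the practice. Elsewhere the plan says plainly that practices are the clusters. A reader might infer that the plan will resample providers and that its mediation intervals will therefore be 27% too narrow with 85% coverage. The documents do not support that: those two figures need provider resampling to be adopted, all clustering to sit at practice level, and the target to be a between-arm contrast. For an indirect effect, the simulated cost of provider rather than practice resampling is about 5 points of coverage (86% against 91%). With an equal split it is about 2 points, close to simulation noise, and with purely provider-level clustering there is no loss. Adjusting for practice-level mediators could also leave a residual practice ICC below 0.04. Practice resampling itself fell short of 95%. The analysis is secondary, and the sentence about components rests on the size of a proportion, not on its interval.

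All of this limits the size of the problem and stands. It does not remove it. Section 12.4 nowhere says which unit will be resampled. Purely provider-level clustering would run against the plan's own within-practice ICC. The general remarks on random effects and on more than one cluster level concern other models and do not set the bootstrap unit. The text also permits the ordinary child-level bootstrap, which does worse than provider resampling.

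**Conclusion.** The point holds as a gap with a conditional consequence. The plan does not fix the resampling unit, and the one cluster level it mentions is below the randomised unit. If providers or children are resampled, the intervals are too narrow to the extent that clustering is at practice level. At ICC 0.04, the SE ratio for a between-arm contrast with provider resampling runs from 0.73 to 1.00. It is 0.61 for child resampling when all clustering is at practice level. Simulated coverage for an indirect effect in that case was about 86% and 81%, against 91% with practice resampling. The simulated figures rest on assumed path coefficients, an assumed mediator ICC and continuous variables, so they show direction and rough size only. The primary GEE analysis and the sample size are not affected. The change should be made, because it is cheap and bears on secondary objective 2.

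**What to change.** State in section 12.4 that all mediation confidence intervals, for path effects and for proportions mediated, use a cluster bootstrap that resamples whole practices within arm (9 per arm), with providers and children kept nested in their practice. Add that with 18 clusters even these intervals may fall somewhat short of 95% coverage, so path effects and proportions mediated will be interpreted cautiously.

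This costs about two sentences. The intervals will be wider, by how much depending on the practice share of the clustering; in the simulated case with all of it at practice level, 0.179 against 0.150 with provider resampling. The plan says that the package has a cluster option but not whether it can resample within arm, so this should be confirmed. If it cannot, the resampling needs a small amount of separate programming.

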4.1 Study participants

Subjects will be pediatric providers (Pediatricians/Nurse Practitioners) and parent/caregivers and their 3-6 year old children from 18 primary care practices located in Ashtabula, Cuyahoga, Geauga, Lorain, Medina, and Portage counties in Ohio (see Table 4.1.1 below). One additional practice not included in the table, Premier Pediatrics, has also agreed to participate and will be included if needed to replace a practice. The majority of the practices are in Cuyahoga County (67%) and the remaining 33% are in surrounding counties in NE Ohio. All practices serve $\geq 20\%$ Medicaid eligible children (9 practices with 20-40% and 9 practices with $> 40\%$ Medicaid-eligible children) and are from the Rainbow Care Connection (RCC). The study is offered to all pediatricians/nurse practitioners in the recruited practices and will be offered to all eligible caregivers and their children excluding those with serious medical or behavioral conditions which would preclude them from participating in the dental screening. All provider and parent participants meeting the eligibility criteria will be enrolled in the study upon signing the consent form.

Table 4.1.1 Practice Information

Practice/Site	# Pediatricians	# Nurse Practitioners	Medicaid Patients (age 3-6)	Medicaid Patients w/WCV (age 3-6)	% Medicaid	County
Ashtabula Pediatrics	1	2	592	448	63%	Ashtabula
Chardon Pediatrics	4	1	387	267	34%	Geauga
Elyria Pediatric Care	3	0	205	168	33%	Lorain
Healthy Kids Pediatrics	1	1	121	95	31%	Portage
[name]	1	0	344	340	80%	Cuyahoga
Medina Pediatrics	4	2	338	250	23%	Medina
NEON	5	0	1856	357	80%	Cuyahoga
Otis Moss	2	0	297	233	82%	Cuyahoga
Pediatric and Adolescent Health Professionals	3	0	157	118	22%	Cuyahoga
Pediatric Partners of Cleveland	2	0	209	165	40%	Cuyahoga
Pediatric Services - Parma	8	0	740	588	30%	Cuyahoga
Pediatriccenter – Garfield	2	0	561	384	24%	Cuyahoga
Rainbow Ambulatory Clinic	4	0	2728	2361	86%	Cuyahoga
Rainbow Euclid Pediatrics	1	0	246	186	68%	Cuyahoga
Suburban Pediatrics - Shaker	7	0	408	335	23%	Cuyahoga
University Premier Pediatricians – Euclid	4	1	504	418	49%	Cuyahoga
UH Westshore Primary Care **	4	0	424	185	45%	Cuyahoga
University Pediatrics of Lorain	4	0	653	523	61%	Lorain
Totals	60	7	10,302	7,421		

Practice information data captured 1/1/2016 through 12/31/2016.

**Data captured 1/1/2017 through 5/31/2017

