5.4 Treatment Assignment Procedures

5.4.1 Randomization Procedures

Eighteen practices (comprising the clusters) will be included in the study. Practices will be randomized to one of the two arms using a restricted randomization scheme with the constraint that 9 practices will be assigned to each arm. This approach will involve the computation of a balance score (for each candidate randomization) based on marginal differences in three key

practice-level variables: % Medicaid-enrolled patients [20% to 40% and >40%], ratio of patients to providers, county [Cuyahoga vs. other]). We use the first generated (constrained) randomization that provides good balance according to a pre-selected balance criterion; it may be reasonable to require perfect marginal balance, if (as we expect) there are a reasonably large number of randomizations that yield this.

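### The plan does not say whether the three factors that constrain randomisation enter the primary model, or which reference distribution the test uses; leaving the factors out would make the test conservative if they predict attendance

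*Combined protocol and SAP*

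**What the plan says.** Sections 5.4.1 and 12.2 allocate 18 practices, nine per arm, by restricted randomisation. The balance score uses "three key practice-level variables: % Medicaid-enrolled patients [20% to 40% and >40%], ratio of patients to providers, county [Cuyahoga vs. other". On selection, section 5.4.1 says: "We use the first generated (constrained) randomization that provides good balance according to a pre-selected balance criterion".

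Section 12.4 sets the primary test: a proportional-odds GEE on a 0/1/2 attendance score, clustered by practice. Its covariates are the arm indicator and "a set of baseline variables representing potential confounders". Later in the same section, under the adjustment paragraph, comes the only named list: "Estimated intervention effects will be adjusted for the following baseline socio-demographic variables: child's age, race, and caregiver SES, education, and marital status".

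On inference, section 12.4 says that a standard-error correction, named only by example, "will be used to adjust for a small number of clusters and 95% confidence intervals will be computed". It gives no z, t or randomisation reference and no degrees of freedom. The only distribution named for this outcome is in section 12.2, which supposes "use of a two-sided 0.05 alpha level z test (with pooled variance) for a difference in proportions" as a simplification for the power calculation, on a binary endpoint.

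No section carries the restriction on allocation into the analysis.

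**The concern.** Restricted allocation keeps the arms alike on the three factors. If those factors predict attendance, the arm difference varies less over the allowed allocations than it would over all allocations. A model without the factors still counts their variance as between-practice error, so its standard error is too large, its interval too wide and its p-value too high.

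The unstated reference distribution matters too with 18 clusters. The two-sided 5% critical value is 1.960 for z, 2.120 for t on 16 degrees of freedom (18 practices less intercept and arm) and 2.160 for t on 13 (less three factors as well). The wording permits at least four primary analyses: factors out or in, with t or z. Their errors run in opposite directions, so a result near the threshold could turn on an unwritten choice.

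**Working it through.** **1. The plan's own power figure.** Inputs from section 12.2: 0.46 v 0.30, 512 per arm, 25% dropout, ICC 0.04, nine practices per arm.
- Retained: 512 × 0.75 = 384 per arm, so 384/9 = 42.67 per practice.
- Design effect: 1 + 41.67 × 0.04 = 2.667. Effective n: 384/2.667 = 144 per arm.
- Pooled z test: power 80.2%. The stated 80% reproduces.

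**2. Standard error, analytically.** The between-practice share of the variance of an arm mean is 42.67 × 0.04/2.667 = 0.64. If the factors are fully balanced and explain a share R² of between-practice variance, a model without them inflates the standard error by 1/√(1 − 0.64 R²):
- R² = 10%: 1/√0.936 = 1.03
- R² = 25%: 1/√0.84 = 1.09
- R² = 50%: 1/√0.68 = 1.21

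**3. Assumptions for the simulation.** R² and the balance criterion are not in the documents, so both are varied. Section 4.1 gives "9 practices with 20-40% and 9 practices with" a higher share, and Table 4.1.1 has 12 Cuyahoga practices and 6 others. Of the 48,620 possible 9/9 allocations, two illustrative criteria allow:
- Tight: county exact, Medicaid stratum differing by 1, difference in mean log(Medicaid patients per provider) at most 0.1. This allows 3,228.
- Loose: county differing by at most 2, Medicaid by at most 3, log-ratio by at most 0.5. This allows 34,596.

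Each simulated trial draws one allowed allocation, with 43 children in every practice. Control P(score ≥ 1) = 0.30 and P(score = 2) = 0.12, the latter assumed. The common odds ratio is (0.46/0.54)/(0.30/0.70) = 1.99; the null uses 0.38 in both arms. The practice variance on the logit scale is 0.04/(0.38 × 0.62) = 0.170, of which R² comes from an equal-weight sum of the three standardised factors. The analysis is the proportional-odds GEE with a small-sample correction. There are 40,000 trials per cell (Monte Carlo SE about 0.001 for type I error, 0.002 for power).

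**4. Results** (tight / loose).

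| R² | Type I, omitted, t16 | Type I, omitted, z | Power, omitted, t16 | Power, included, t13 | Power, randomisation test |
|---|---|---|---|---|---|
| 0% | 0.040 / 0.041 | 0.057 / 0.057 | 72 / 72% | 69 / 65% | 72 / 74% |
| 10% | 0.035 / 0.036 | 0.049 / 0.050 | 72 / 72% | 71 / 67% | 75 / 74% |
| 25% | 0.026 / 0.033 | 0.038 / 0.046 | 73 / 73% | 76 / 73% | 79 / 77% |
| 50% | 0.014 / 0.022 | 0.022 / 0.033 | 74 / 73% | 84 / 81% | 86 / 80% |

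The 0.040 at R² = 0 comes from the correction plus t, not from the omission; only the fall below it does. With the factors included, type I error is 0.034–0.042 (t13) or 0.052–0.061 (z). The randomisation test holds 0.045–0.047 throughout. Interval width, omitted t16 relative to included t13, is 0.96/0.99/1.04/1.15 (tight) and 0.92/0.95/1.00/1.10 (loose) in the order of the table.

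**5. Cross-checks, omitted with t16, same order.**
- Cluster-mean regression: 0.049/0.043/0.034/0.018 (tight), 0.049/0.047/0.042/0.030 (loose).
- Binary logistic GEE: 0.042/0.036/0.029/0.015 (tight), 0.041/0.039/0.032/0.026 (loose).
- Proportional-odds GEE with a child-level covariate: 0.036/0.032/0.026/0.015 (tight), 0.035/0.033/0.030/0.022 (loose).

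The decline with R² appears in each.

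**The case against.** The strongest case against acting is that the effect is small and its direction mostly benign. All enrolled children are on Medicaid, so R² may well be low. At 0–10%, adding the factors costs 1 to 3 points of power under tight balance and 5 to 7 under loose. At 25% under loose balance the two models tie. All of this stands, and it is why tight and loose results must be read together.

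Equal practice size is also only an approximation, as section 12.2 says. Section 5.3's recruitment factors give 0.25 × 0.95 × 0.95 = 0.226 of each practice's annual well-child visits in Table 4.1.1. Eight practices then fall short of 57, and the smallest yields 95 × 0.226 = about 21. With sizes capped that way (binary GEE, 4,000 trials per cell), type I error with the factors included was about 0.05 with t13 and 0.067–0.078 with z. So the included figures above apply to equal sizes only, and z may be more liberal in practice.

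Stronger readings that the documents do not support:
- *The factors are definitely omitted.* The confounder wording in section 12.4 is open. Elsewhere the protocol calls child medical illness (3.2.3) and provider socio-demographics (8.1.3) confounders, and those are not in the named list either. This is silence, not proven omission.
- *A z test is planned.* The z in section 12.2 belongs to a simplified binary power calculation.
- *The trial falls short of its 80% power.* That figure comes from an unadjusted calculation and reproduces.
- *The randomisation broke its own rule because nine practices per Medicaid band cannot split evenly into nine per arm.* Section 5.4.1 offers perfect balance only as something that may be reasonable, not as the criterion.

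**Conclusion.** The gap is real: the design restricts allocation on three factors, the named adjustment list contains none of them, and the primary test has no stated reference distribution. Following the list makes the test conservative to the extent that the factors predict attendance. The loss is nil or negative at low R², 0 to 3 power points at R² = 25%, and 8 to 10 at 50%, comparing t16 without the factors to t13 with them. The separate choice of z would be mildly liberal when the factors explain little or are included. These sizes rest on an assumed R², two illustrative balance criteria, an assumed P(score = 2) and equal practice sizes. The direction does not depend on the exact values. The point should be settled, but it does not threaten the trial's validity.

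**What to change.** Before arm-level outcomes are seen, adopt one of two equally acceptable options, in the same words in the primary-model and adjustment paragraphs of section 12.4.

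- **A.** Take the primary p-value from a randomisation test over the allocations that the balance criterion allowed. Keep the GEE odds ratio as the estimate and state how the interval is obtained.
- **B.** Include % Medicaid stratum, county and patient-to-provider ratio in the primary GEE beside the listed socio-demographics, with a t reference on stated degrees of freedom (13) rather than z.

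Under either option, record the balance criterion used, how many allocations it allowed, and the ratio's numerator and values for the practices as randomised. The documents alone cannot supply these. The numerator is undefined. The Medicaid-patient column of Table 4.1.1 sums to 10,770 against a printed 10,302. One practice's counts carry the note "Data captured 1/1/2017 through 5/31/2017", while the rest cover all of 2016.

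This is a cheap improvement: wording plus a record, with no new data. B costs about 3 (tight) to 7 (loose) points of power if the factors are not prognostic, with break-even near R² = 10% and 25% respectively. A requires the allowed set to be rebuilt from the randomisation record, with at least 40 allocations for a two-sided p of 0.05 to be attainable (2/40).
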